## I. Research Background

As one of the components of traditional medicine, acupuncture and moxibustion is widely used at home and abroad due to its exact curative effect and no toxic side effects. It has been widely accepted and used in 183 countries and regions around the world. However, the biological basis and intrinsic mechanism of acupuncture and moxibustion have not been fully explained, although high-quality papers have been published in succession. With the continuous innovation of life science research technology and the deepening of modern research on acupuncture and moxibustion, the mysterious veil of the effect law and mechanism of acupuncture and moxibustion has been gradually unveiled. For example, academician Han Jisheng and his team have applied neurobiological techniques to prove that there are differences in the analgesic effect and onset time of different frequencies of electroacupuncture. The intrinsic biological basis may be related to the release of different types of central opioid peptides at different times and different parts promoted by different frequencies of electroacupuncture. Recently, [name] team at Harvard University revealed the regional specificity of electroacupuncture stimulation by using biological technologies such as lentivirus technology and gene mice, and found that there were different biological bases for the anti-inflammatory effects of electroacupuncture at different depths and intensities. The research results were published in *Nature* and *Neuron*. The international academic status of acupuncture has also been further improved. Therefore, the biological basic research of acupuncture and moxibustion plays a pivotal role in both the explanation of the mechanism of traditional acupuncture and moxibustion and the promotion of its further development.

The traditional theory of acupuncture and moxibustion is continuously summarized and refined based on the clinical practice experience of predecessors. Although the clinical efficacy is stable and widely used, there is still a lack of objective evidence and biological basic research. Therefore, on the basis of the summary of previous experience, it is particularly important to deeply reveal the intrinsic biological basis of the classic discussion of acupuncture and moxibustion through modern scientific research technology. In addition, although the human disease model is constructed through animal experiment simulation, a part of the therapeutic mechanism of acupuncture and moxibustion can be explained by comparing the physiological and biochemical indexes and functional indexes of the model animals in each group. However, the ideology and social attributes of human beings directly lead to insurmountable huge differences between human beings and animals. Therefore, clinical trials based on human beings are still an indispensable part.

It is mentioned in *Neijing* (The Classic of Internal Medicine) that Weizhong acupoint is used to treat waist diseases. It is recorded in *Plain Questions*: "The foot Taiyang pulse causes low back pain, citing the back of the neck ridge as the severe form, and needling it at Zhongtaiyang for severe bleeding". After the summary and summary of many doctors, the basic symptoms of Weizhong acupoint were refined as waist and leg symptoms in the Song Dynasty, and then continued to summarize and summarize. Then, the "Wei zhong qiu" in the song of the four general acupoints in the Complete Compendium of Acupuncture and Moxibustion, which is still in use today. In clinical practice, bloodlet therapy, electroacupuncture, moxibustion and other methods are often applied at Weizhong point to treat various lumbar disorders, and good effects are obtained. The existing studies have preliminarily shown that there is some objective relationship between the waist and back and Weizhong point. For example, the stimulation of Weizhong point can observe the rich local blood supply, the increase of local temperature, and the improvement of waist muscle fatigue resistance. When the waist and back lesions occur, acupoint sensitization phenomena such as force sensitivity, heat sensitivity and local electrical resistance changes can also be observed at Weizhong point. However, the specific association between Weizhong point and waist and back still needs to be further explored and improved. Therefore, this study intends to take the connotation study of "Weizhong acupoint on waist and back" as the entry point, to explore the correlation between the waist and Weizhong acupoint through infrared thermal imaging technology, and to explore the differences in the image of the waist observation area by different intervention methods, in order to provide some reference for the interpretation of its scientific connotation.

## **II. Main research content, objectives, program and progress, and key problems to be solved:**

### **1. Research Content**

The healthy people were selected as subjects and treated with moxibustion. FLIR E53 infrared thermal imager was used as the observation instrument to detect the dynamic changes of skin temperature in a specific area of the waist after different interventions (acupuncture

and moxibustion) at different acupoints (Weizhong point and Chize point), in order to further explore the relationship between the waist and Weizhong point. To provide an objective research basis for enriching the scientific connotation of "waist and back".

## **2. Objectives of the study**

To explore the relationship between the waist and Weizhong points and whether acupuncture and moxibustion have different effects on the observation area of waist by observing the changes of local average temperature of waist in healthy subjects after applying acupuncture or moxibustion to different points.

## **3. Study PROTOCOL**

The investigator clearly and orally explained the study and its potential risks and benefits to the subject before starting the study. After obtaining consent from the patient or his or her authorized person, the patient or his or her authorized person and the investigator signed and dated the informed consent form. Patients or their authorized persons could be screened for participation in the study only if they had provided written informed consent.

### **3.1. Study Protocol**

Subjects were screened strictly according to the diagnostic criteria, inclusion criteria and exclusion criteria. After confirmation of enrollment, they were randomly divided into groups

according to the random number table until the total number of observation was completed.

Healthy subjects aged 18-40 years old from Zhejiang Chinese Medical University were included in this study.

### 3.1.2. A randomized controlled trial was designed and conducted

(1) Healthy subjects were randomly assigned by SPSS 20.0 software program. The 180 digits were randomly divided into a moxibustion group at Weizhong point, a moxibustion group at Chize point, an acupuncture group at Weizhong point and an acupuncture group at Chize point according to the ratio of 1:1:1:1. The grouping information was kept confidential by the project leader.

(2) The random allocation card was prepared as follows:

Association between Weizhong point and waist and back based on
infrared thermal imaging technology
No. :
Groups:
Methods of intervention:

(3) The random assignment card is sealed in an envelope with the same number recorded

on the envelope as the card.

(4) Arrange the envelopes containing the randomization cards in order of number

(5) The randomization cards were made and kept by the investigators and distributed to

the operators during the study. When eligible subjects entered the study, the operator

opened the same numbered envelopes in the order in which they entered and grouped

according to the rules of the cards inside the envelopes without making any changes.

Participants in the group assignment did not participate in the statistical analysis of the

data. Data extraction and statistics were collected and sorted by the personnel who did

not know the grouping, and the researchers, operators, and statisticians were separated.

### **3.1.3. Inclusion criteria**

① Age  $\geq 18$  years old, both sexes,  $18.5 \leq \text{BMI} \leq 23.9 \text{ kg/m}^2$ ;

② Previous good health without organic diseases;

③ Understand the study process voluntarily participated in the study and signed the informed consent form.

### **3.1.4. Exclusion Criteria**

① Women who are menstruating, pregnant, or breastfeeding;

② Unable to complete the filming in a prone position;

③ Those with skin diseases or skin damage, sensory disorders, scars or vegetations at

the test points;

- ④ Patients with serious systemic diseases, or those considered by the investigators to be unsuitable for the study;
- ⑤ Patients with epilepsy, head injury or other related neurological diseases.

### **3.1.5. Exclusion and expulsion criteria**

Exclusion criteria (those who have been enrolled but meet one of the following criteria should be excluded) : (1) Those who do not meet the inclusion and exclusion criteria are found in the trial; (2) obvious adverse reactions occurred during the treatment; (3) The subjects were not treated according to the treatment plan after enrollment. Note: The excluded cases should be explained, and the original medical records should be kept for future reference. No statistical analysis of efficacy will be performed, but those who have received at least one treatment and have records can participate in the analysis of adverse reactions.

Drop-out criteria (patients who had been enrolled but had not completed the clinical protocol were considered drop-out in the following circumstances) : (1) patients withdrew or lost follow-up; (2) Serious adverse reactions or adverse events occurred during treatment.

Note: The reasons for dropouts should be explained, and the study medical records should be kept for future reference. Data were not carried forward at follow-up.

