### **3.2.5. Efficacy indicators and evaluation**

- (1) Baseline MEASURES: Through interviews and questionnaires, the subjects' gender, age, weight, height, frequency (weekly) of waist discomfort (such as waist acid, etc.), and whether they had received acupuncture/moxibustion related treatment were collected. Before the intervention, the average temperature of waist observation area (the geometric figure surrounding the second lateral line of bilateral bladder and the horizontal lines of T12 and S1) was recorded by infrared thermal imaging instrument.
- (2) The main outcome measures were the average temperature changes in the waist

observation area (the geometric figure surrounded by the second lateral line of bilateral bladder and the horizontal lines T12 and S1) 30 minutes after the intervention and immediately after the intervention

(3) Secondary outcome measures:

- ① The highest temperature in the designated area of the waist 30min after applying the intervention;
- ② The average temperature change value of the designated area of the waist was measured 5 min and 15 min after intervention.
- ③ The average temperature of local acupoints ( $\phi=2\text{cm}$ ) at Weizhong and Chize before intervention and 30 min after intervention were recorded.
- ④ Evaluation of waist warm sensation: Binary data (yes/no) and NRS score (0-10) were used to record the waist warm sensation and its intensity during the intervention.
- ⑤ The differences of pain threshold before rest and immediately after the intervention were compared at Shen双shu (BL 23), Zhishi臍 (BL 52), Mingmen (GV 4) and Weizhong (BL 40).

(4) Safety evaluation: the adverse reactions and their manifestations, occurrence time, degree, treatment measures, process and outcome were recorded, and the correlation

between the adverse reactions and the treatment was judged.

(5) Compliance evaluation: the drop-out situation and reasons were recorded and analyzed.

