## **6. Statistical analysis**

### **1. Statistical software**

The data were analyzed by a third party statistician who was not involved in the preliminary study. Statistical software (SPSS 26.0) was used for statistical analysis.

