### 3. Statistics of data

All the results were analyzed with the use of SPSS, version 23.0. All statistical tests were two-sided, and a  $P$  value of less than 0.05 was considered to indicate statistical significance. Normally distributed continuous variables were compared among the four groups using analysis of variance (ANOVA), and non-normally distributed variables were compared using the Kruskal-Wallis H test. If normal transformation could not be performed, the rank-sum test was used for comparison. Count data were compared using the chi-square test. Pearson correlation analysis was used for correlation analysis. Ordered logistics regression analysis was used to analyze the influence of general data on the final data. The factorial test focused on the main effects of the two treatments and their interaction. Therefore, repeated measures ANOVA with factorial design was used to analyze the differences in the effects of different treatments and different intervention acupoint areas on the observation area, and Sidak test was used for comparison between groups.

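### The factorial repeated-measures ANOVA, as usually run, leaves out any volunteer with a missing waist reading, and the plan says nothing about how drop-outs' partial data are used

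*Combined protocol and SAP*

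**What the plan says.** Section 3.1.5 separates two groups. Excluded cases were enrolled but found ineligible, had obvious adverse reactions, or were not treated to plan; for them, "No statistical analysis of efficacy will be performed". Drop-outs have their own paragraph: "patients withdrew or lost follow-up", or a serious adverse reaction or event. On their data the plan says only "Data were not carried forward at follow-up". It does not say whether readings taken before drop-out are used.

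Section 3.2.5 takes a baseline waist image. It defines the main outcome as the change in average waist temperature "30 minutes after the intervention and immediately after the intervention". Among the secondary outcomes, "The average temperature change value of the designated area of the waist was measured 5 min and 15 min after intervention".

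Section 6.3 says that "repeated measures ANOVA with factorial design was used to analyze the differences in the effects of different treatments" and acupoint areas on the observation area, with Sidak comparisons between groups. It also names an ANOVA across the four groups for normally distributed continuous variables, and a rank-based test otherwise. Section 6.1 gives SPSS 26.0 and section 6.3 gives version 23.0. No section names imputation, a mixed model, an analysis set or a sensitivity analysis.

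**The concern.** A conventional repeated-measures ANOVA needs a value at every level of the time factor. If one is missing, the participant leaves the model, including the valid readings. Carry-forward is ruled out and nothing replaces it, so a volunteer imaged immediately after the session but not at the last time would contribute nothing to the model that addresses the factorial question. If the 5 and 15 min readings are modelled too, one unusable secondary image would also remove both main-outcome readings from that model.

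Two things are at stake. The first is precision, since valid main-outcome readings go unused. The second is the assumption behind the result. A completers-only comparison is safe if, within each arm, leaving is unrelated to the temperature response. A likelihood-based model that uses all observed readings also allows leaving to depend on readings already taken. The arms receive different stimuli with different listed harms (burns, subcutaneous bleeding), so the stricter assumption should not be taken for granted.

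**Working it through.** **1. The plan's sample size and its slack.** Inputs from section 3.1.1: two-sided α = 0.05, power 80%, σ = 1.17 °C. The difference that reproduces the stated size is acupuncture versus moxibustion at Weizhong, δ = 1.4 − 0.7 = 0.7 °C.

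n = 2[(u_α + u_β)σ/δ]² + u_α²/4 = 2[(1.960 + 0.842) × 1.17/0.7]² + 1.960²/4 = 43.85 + 0.96 = 44.81, which rounds up to 45.

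This matches the stated 45 per group (180 in total). Nothing is added for attrition, so each participant lost from the model comes straight off the 45.

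**2. Who leaves the model.** The rows follow from the method, on the usual complete-row implementation.

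| Readings available | Factorial repeated-measures ANOVA | Four-group ANOVA at the immediate time |
|---|---|---|
| All modelled readings | Used | Used |
| Immediate present, 30 min missing | Left out | Used |
| Both main readings present, 5 or 15 min missing | Left out if all times are modelled | Used |

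**3. How many, if people leave and do not return.** The attrition rate is an assumption; the documents give none. Drop-out is monotone: a person who leaves misses every later image. If a share p has gone by the last image, the share lost is p, however many times are modelled.

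- p = 1%: 180 × 0.01 = 1.8, about 2
- p = 2%: 180 × 0.02 = 3.6, about 4
- p = 3%: 180 × 0.03 = 5.4, about 5

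**4. How many, if single images are unusable.** If each of k post-intervention images is independently missing with probability p (again assumed), the share lost is 1 − (1 − p)^k.

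| p per image | k = 2 (main readings only) | k = 4 (with 5 and 15 min) |
|---|---|---|
| 1% | 2.0%, about 4 of 180 | 3.9%, about 7 of 180 |
| 2% | 4.0%, about 7 of 180 | 7.8%, about 14 of 180 |
| 3% | 5.9%, about 11 of 180 | 11.5%, about 21 of 180 |

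With k = 2, the share of lost participants who miss both main readings is p²/[1 − (1 − p)²]. At p = 3% that is 0.0009/0.0591 = 1.5%, so nearly all of them have one valid main reading.

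**5. Effect on power.** For δ = 0.7 and σ = 1.17, with whole participants removed from 45 per group:

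| Loss | n per group | Power, normal approximation | Power, noncentral t |
|---|---|---|---|
| 0% | 45 | 81.0% | 80.1% |
| 2% | 44.1 | 80.2% | 79.3% |
| 5% | 42.75 | 79.0% | 78.1% |
| 10% | 40.5 | 76.8% | 75.8% |

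These figures are for a two-group comparison of means, the basis of the plan's own calculation, not for the full factorial model.

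**6. The time factor is not settled.** Each intervention lasts 30 min (sections 3.2.1 to 3.2.4). Section 3.2.5 places the main readings immediately and 30 min after the intervention, but dates the maximum temperature to 30 min after the intervention is applied, which could be the end of the session. Section 6.3 does not list which times enter the repeated-measures model. Whether k is 2 or 4, and whether some readings fall within the session, cannot be read from the text.

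**The case against.** The strongest reply is that the plan never says incomplete participants are deleted. It names a method and a software package, not a procedure or a complete-case rule. That is correct: deletion is inferred from how the method is normally run, with no alternative given.

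A reader might infer that a partial drop-out loses every valid reading from all analyses. The documents do not support that. Section 6.3 also names a four-group ANOVA, which could use a reading at a single time, and it does not call the repeated-measures model primary. A single-time test would not, however, supply the factorial analysis over time.

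A reader might also take the figures of 7 to 21 of 180 as the effect of drop-out. They are not. They require scattered unusable images, which section 3.1.5 does not address, and all four readings in the model, which section 6.3 does not state.

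The affected group is narrow: healthy volunteers, a 30 min intervention, no longer follow-up described, and people who cannot complete filming prone are not enrolled. Some early leavers may also fall under the separate exclusion rule, particularly if the later readings lie within the session. All of this limits the size of the problem. It does not supply the missing rule for drop-outs with partial data.

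**Conclusion.** The point holds as a modest improvement to the analysis. The named model, as conventionally run in SPSS, would leave out volunteers with incomplete readings, and the plan provides nothing else for them. Declining to carry values forward is not the fault; the gap is that no method takes its place.

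The loss is probably small: about 2 to 5 of 180 at 1% to 3% monotone drop-out, and more only if individual images are also unusable. At 2% whole-participant loss, power falls by less than one percentage point; at 5% it falls by about two. Because the sample size has no allowance, even small losses take power to or just below the planned 80%.

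This rests on the usual complete-row implementation, on assumed missingness rates, and on at least two readings entering the model.

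**What to change.** - **Section 6.3:** for waist temperature, replace the factorial repeated-measures ANOVA with a linear mixed model for repeated measures. Use method, acupoint, time and their interactions as fixed effects, an unstructured covariance and restricted maximum likelihood. Sidak comparisons can stay.
- **Section 3.1.5:** keep the rule against carrying values forward, and add that every reading obtained before drop-out is analysed in the randomised arm.
- **Section 3.2.5:** reconcile the reading times with the 30 min intervention, and list in section 6.3 the times that enter the model.

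The cost is wording in three places; SPSS can fit the model and no new data are needed. With complete data the conclusions should be similar. The downsides are that the model relies on missing-at-random and on a stated covariance structure. It also recovers a missing 30 min reading only in part, through its correlation with earlier readings. A volunteer who leaves before any post-intervention image gains little from the change.

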### **3.1.6. Termination criterion**

(1) Specialists will be responsible for the evaluation of severe adverse reactions during the study to determine whether to continue or terminate the study;

(2) if the subjects developed serious complications or other serious diseases during the study period and needed to take emergency measures;

(3) the subjects could not continue the study for other reasons.

### 3.1.7. Adverse events

Adverse events and the reasons for dropouts were recorded in detail.

## 3.2. Interventions

In this study, the subjects were randomly divided into a moxibustion group at Weizhong point, a moxibustion group at Chize point, an acupuncture group at Weizhong point, and an acupuncture group at Chize point at a ratio of 1:1:1:1 for a randomized controlled trial to observe the relationship between waist and Weizhong point. Proposed research time: January 1, 2023 to December 31, 2023. Specific treatments are as follows.

### 3.2.1. Acupuncture at Weizhong acupoint group:

- ① Acupoint selection: Bilateral Weizhong (BL40)
- ② Location: Refer to the national standard of the People's Republic of China (GB/T 12346-2006) "Acupoint Name and Location"
- ③ Acupuncture operation: The acupuncture needles of φ25×40mm Huatuo brand were

selected and sterilized at Weizhong points with 75% alcohol. Acupuncture was performed avoiding the nerves and blood vessels. The depth of the needles was about 1 cun (33mm). When the subject had deqi sensation such as acid, numbness, and swelling pain, the manipulation was stopped, and the needle was retained for 30 minutes. No manipulation stimulation was given during the retention period.

- ④ The intervention time was 30 min

### **3.2.2. Acupuncture Chize acupoint group:**

- ① Acupoint selection: Bilateral Chize (LU5)
- ② Location: Refer to the national standard of the People's Republic of China (GB/T 12346-2006) "Acupoint Name and Location"
- ③ Acupuncture operation: the same as Weizhong point operation.
- ④ The intervention time was 30 minutes

